7 TRIAL PARTICIPANTS

7.1 Overall Description of Trial Participants

Each site will recruit patients with acute breathlessness. Final confirmation of the primary indicator diagnosis is usually available at discharge (following visit 1b) and after further diagnostics at the stable state follow up clinic (at visit 2). The final primary indicator diagnosis and additional comorbidities will be recorded at initial senior clinical review, discharge and at follow up. The indicator diagnosis will be used to define the number of patients recruited within each disease stratum.

The study will have two distinct phases:

Phase 1: Discovery of novel breath metabolomic biomarkers.

Phase 2: Replication and validation of selected biomarkers in Phase 1.

Planned recruitment to meet the primary, secondary and exploratory study endpoints is outlined below.

- (i) Acute Heart failure (n=55-100 Phase 1, n=55-100 phase 2)
- (ii) Adult community acquired pneumonia (n=55-100 Phase 1, n=55-10 Phase 2). This condition will be defined as new radiological consolidation responsive to treatment according to the British Thoracic Society (BTS) community acquired pneumonia guidelines.
- (iii) Adult exacerbations of airway diseases asthma and COPD (n=110-200 Phase 1, n=110-200 Phase 2). This condition will be defined as a clinician diagnosis with subsequent or historical evidence of objective diagnostic criteria according to national and international guidelines.
- (iv) Paediatric exacerbations of acute childhood wheeze and/or confirmed asthma (n=55-100 Phase 1, n=25-50 Phase 2).

This condition will be defined as a clinician diagnosis and for childhood wheeze/asthma subsequent or historical evidence of objective diagnostic criteria according to national and international guidelines.

(v) Age/environment matched Adult/spousal/parental/ sibling volunteers (n=55-150 adults/50 children) discovery phase, (n=55-75 adult/25 children)

replication phase) with no evidence or history of the indicator disease being evaluated in their spouse/sibling/child.

(vi) Stable state participants with a confirmed diagnosis of asthma, COPD or heart failure that have not had and exacerbation of their disease within the preceding 6 weeks (n=200 (100 in each phase)).

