2. SYNOPSIS

Trial Design Pr	onsor Reference 0569 ospective Acute Care 'Real Life' Observational Study
Trial Participants Pa	
со	tients with acute breathlessness in the following (post-acute pathway nfirmed) strata:
1 * *	Acute Heart failure , characterised by a clinician diagnosis, and a proto-typical sponse to treatment.
re	Community acquired pneumonia , defined as new radiological consolidation sponsive to treatment according to the British Thoracic Society (BTS) mmunity acquired pneumonia guidelines.
wi pr) Adult exacerbations of asthma and COPD, defined as a clinician diagnosis th objective confirmatory evidence of disease based upon historical or ospective measurements, requiring an acute change in treatment (e.g. tibiotics, oral corticosteroids or increased bronchodilator therapy)
(iv) Paediatric exacerbations of acute childhood wheeze and or confirmed asthma
he an wi	Age and/or Home environment matched Adult/Sibling/Parent/Spousal althy volunteers, who have no prior history of asthma, COPD, heart failure d have not been admitted to hospital with community acquired pneumonia thin 6 weeks of the baseline study visit. Additional healthy volunteers will also recruited from local databses.
as) Stable state aged matched participants with a confirmed diagnosis of thma, COPD or heart failure, that have not had and exacerbation of their sease within the preceding 6 weeks.
Planned Sample Size Ar	interim analysis was conducted in September 2017 to determine the sample
siz	e of the ember acute study. Guided by literature search, a panel of 10 pre
sp	ecified aldehyde biomarkers derived from GCMS analysis were supplied. The
bio	omarkers were normalised to a common standard and were not background
su	btracted.
A	closed formula from Hsieh et al, Statis med 1998, was utilised to calculate
sa	mple sizes from logistic regression models of the 10 aldehydes with acute
br	eathlessness as the outcome measure. The sample size estimates are also
re	evant to acute class comparisons vs. the sum of other acute classes.
Ва	sed upon the samples size estimates we would have an 80% power at the 5

	% significance level to detect an odds ratio of association of 1.2 for a given
	disease class with minimum of 55 patients per disease class.

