5.2 Secondary Objectives

- To replicate selected metabolomic breath biomarker panels of acute breathlessness using a combination of both (i) discovery technologies (including GC-MS) and (ii) point of care auto tuned breath sensing devices (including linear IMS, CMS, PTR-MS).
- To evaluate the primary endpoint stratified by breathlessness as follows (i) change in eMRC by 1
 unit, (ii) patient defined breathlessness and (iii) 100 mm visual analogue score for breathlessness
- To discover and replicate metabolomic breath biomarkers that differentiate (i) Acute Heart failure,
 (ii) Community acquired pneumonia, (iii) Adult exacerbations of asthma and COPD
- To quantify the level of clinical uncertainty in the primary diagnosis using a 100 mm visual analogue scale and independent clinical adjudication of case notes blinded to the following blood biomarkers (i) CRP (ii) blood eosinophils (iii) BNP (iv) Troponin-I but not clinical history and chest X-ray.
- To identify and discover metabolomic breath biomarkers of acute childhood wheeze and or confimed asthma.

To clinically validate metabolomic breath biomarkers generated above using a combination of existing pathology markers e.g. BNP, CRP, blood eosinophils and troponin- I and other clinical relevant prognostic scoring tools e.g DECAF, CURB65 and Heart failure risk calculator http://www.heartfailurerisk.org/^[19]

- Replication of acute breathlessness biomarkers will be according to the following predefined primary diagnoses in the replication phase:
 - (i) Acute Heart failure (n=55-100),(ii) Community acquired pneumonia (n=55-100), (iii) adult exacerbations of asthma and COPD (n=110-200),(iv) paediatric exacerbations of acute childhood wheeze and confirmed asthma (n=25-100),(v) age/home environment matched adult/spouse/sibling/parent control subjects (n=55-75 adults/25 children)
 - 5.3 Exploratory End Points (where applicable)
 - 1) To evaluate the dynamic profile of breath biomarkers during (i) the acute state, (ii) in the recovery state post exacerbation.

Page 15 of 46

- 2) To evaluate the relationship between breath metabolomic biomarkers and health status/ functional measures:
- Health status measures
- Physical performance
 - 3) To evaluate the relationship between metabolomic breath biomarkers and clinical outcomes including (i) hospital readmission at time points up to 2 years (ii) response to standard clinical therapy and (iii) death.

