7.2 Inclusion Criteria

- (i) Able to give informed consent for participation in the study.
- (ii) Male or Female, aged 16 years or above (adult cohort) and 5-15 years for paediatric patients attending the acute care paediatric pathway.
- (iii) Capable (in the opinion of the EMBER clinical research investigator(s) of providing serial breath samples.
- (iv) Diagnosed with acute breathlessness as one of the primary indicator reasons by the clinical acute care team. This is not a requirement for healthy subjects or matched controls.
- (v) One of the indicator provisional diagnoses identified in section 7.1 following senior review by the clinical acute care team. This is not a requirement for healthy subjects or matched controls
- (vi) Able (in the Investigators opinion) and willing to comply with all study requirements.
- (vii) Willing to allow his or her General Practitioner and consultant, if appropriate, to be notified of participation in the study.
- (viii) Ability to understand English.

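### Response to treatment is part of the pneumonia class definition (and, in the synopsis only, of heart failure), although response and death are outcomes the biomarkers are to be related to

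*Protocol*

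**What the plan says.** **Class definitions.** Section 7.1(ii) says of adult community acquired pneumonia: "This condition will be defined as new radiological consolidation responsive to treatment according to the British Thoracic Society (BTS) community acquired pneumonia guidelines". The synopsis has the same condition. For acute heart failure the synopsis says "characterised by a clinician diagnosis, and a proto-typical" response to treatment. Section 7.1(i) gives only the planned numbers for heart failure, with no definition. The adult asthma/COPD and paediatric classes have no response condition in either place; they rest on a clinician diagnosis with objective evidence.

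**Timing of the label.** Entry under section 7.2(v) needs "One of the indicator provisional diagnoses identified in section 7.1 following senior review by the clinical acute care team". The synopsis describes the strata as confirmed after the acute pathway. Section 7.1 says: "Final confirmation of the primary indicator diagnosis is usually available at discharge (following visit 1b"), with further diagnostics at visit 2. It has the diagnosis recorded at senior review, at discharge and at follow-up, and then says: "The indicator diagnosis will be used to define the number of patients recruited within each disease stratum". It does not say which of the three is meant.

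**Outcomes.** Exploratory item 3 in section 5.3 relates the biomarkers to readmission, "response to standard clinical therapy and (iii) death". Section 10.1 (Subsidiary Analysis) plans a logistic model for death and Cox, competing-risk and logistic models for readmission.

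**The concern.** A class label that contains a later outcome conditions every within-class analysis on that outcome. A patient with new consolidation who fails treatment, or who dies before response can be assessed, does not satisfy section 7.1(ii) as written. If that label is the one analysed, the question of how biomarkers relate to response and death is put to a group from which part of the poor-outcome tail has been taken.

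The secondary comparison of disease classes (sections 5.2 and 10.1) is exposed too. Section 21.4 gives pneumonia against the remaining categories as an example. Setting a response-selected class against classes with no such condition means that a marker of severity or treatability could pass for a marker of disease. Accuracy would also be reported for more typical cases, although section 4 motivates the study by diagnostic uncertainty and multifactorial presentation.

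**Working it through.** No figure in the protocol is at issue, so the check sets its statements side by side and then sizes the effect under stated assumptions.

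**Reading the statements together**

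1. Response cannot be known at senior review, so only the provisional diagnosis can operate at entry. Yet section 7.2(v) points to section 7.1, whose pneumonia definition needs later information.
2. Three statements bear on who assigns the label. Section 5.1 says the treating physician, for the discovery phase. Section 7.1 has three recorded diagnoses. Section 10.1 has an adjudication panel, whose verdict is nowhere made the class label.
3. Section 10.7 keeps all eligible consented participants in the analysis. No statement says into which class a non-responder or an early death goes.
4. These patients are therefore not removed from the study. They fail to meet the written class definition, and where they go is undefined.

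**Illustration of size**

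Inputs: 55 per class per phase and 110 over both phases (sections 21.2 and 21.5); target sensitivity 80% with a precision of 5–8 points (section 21.3). The share x of a class that does not meet the response condition is not given for pneumonia or heart failure. Assume 5–15%.

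- Patients lost to the label, 55·x: 55 × 0.05 = 2.75 and 55 × 0.15 = 8.25, so about 3 to 8 per class per phase.
- 95% half-width for 80% sensitivity, 1.96·√(0.16/n): 7.5 points at n = 110; 7.7 at n = 110 × 0.95 = 104.5; 8.1 at n = 110 × 0.85 = 93.5. The loss of precision is small.
- Shift in class sensitivity, x·(0.80 − s₀), where s₀ is the sensitivity in those lost. With s₀ assumed to be 0.40–0.60, the shift is 0.05 × 0.20 to 0.05 × 0.40 = 1–2 points at x = 5%, and 0.15 × 0.20 to 0.15 × 0.40 = 3–6 points at x = 15%. If the biomarker works better in sicker patients (s₀ above 0.80), the sign reverses.
- Observed class mortality when a fraction f of deaths precedes any judgement of response: m(1 − f)/(1 − m·f). The only mortality in the protocol is for COPD (section 9.1.5, 14% at three months). Borrowing m = 0.14 purely to show the mechanism, f = 0.25, 0.50 and 0.75 give 0.105/0.965 = 10.9%, 0.070/0.930 = 7.5% and 0.035/0.895 = 3.9%.

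**The case against.** The strongest reply is that nothing in the protocol actually takes a non-responder or an early death out of a class. Entry is on a provisional diagnosis, section 5.1 leaves the discovery-phase diagnosis to the treating physician, all eligible participants are analysed, and a senior-review label is on record. A confirmed final diagnosis is also a recognised reference standard in diagnostic studies. This stands in part. The loss is conditional on the confirmed label setting the class. But the section 7.1(ii) wording and the synopsis's account of the strata as confirmed after the acute pathway both point to that label, and nothing says otherwise.

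The heart failure side is weaker: it rests on one synopsis line.

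The contrast with the other classes is not clean. Asthma/COPD may also depend on later objective evidence, and severe cases in every class are filtered by the ability to give serial breath samples (section 7.2(iii)), by the safety and prognosis exclusion and by consent by visit 1b (section 7.3(iv) and (v)). What remains is that an explicit response condition applies to some classes and not to others.

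A reader might infer that response becomes constant in these classes. The protocol does not define response as yes or no, and the repeated breathlessness scores and CRP in Table 1 can still vary among responders. Range restriction is the supportable claim.

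**Conclusion.** The point holds for pneumonia on the text of section 7.1(ii) and the synopsis, and for heart failure on the synopsis alone. Analysed on the response-confirmed label, the response and death analyses are conditioned on their own outcome, and the disease-class comparison mixes response-selected classes with others.

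The size is unknown from the documents. The 3–8 of 55 per class rests wholly on the assumed 5–15%, and the sensitivity shift rests further on an assumed s₀.

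Three stronger readings are not supported:

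- The two classes make up 110 of the 220 adult acute patients per phase (2 × 55 of 4 × 55), but that counts everyone in them, not those lost.
- The 14% COPD figure is mortality at three months, not death before response can be judged. A pneumonia patient who responds and dies later stays in the class, so 14% of 55 (about 8) is no estimate of the loss.
- The primary analysis contrasts acute breathlessness with recovery and does not use the class label, so any effect there is indirect. Response and death are exploratory or subsidiary outcomes.

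**What to change.** 1. Reconcile the synopsis with section 7.1, so that both say the same about whether response is part of the heart failure definition, and state which recorded diagnosis sets the stratum counts and which sets the analysis class.
2. In section 10.1 (Subsidiary Analysis), assign class for the response, readmission and death analyses by the indicator diagnosis recorded at initial senior review, and keep non-responders and early deaths in that class.
3. For the secondary disease-class comparison, report results by the senior-review diagnosis alongside the response-confirmed diagnosis, with the number of patients whose label differs.
4. Do not replace the response condition for heart failure with BNP. It is a model covariate in section 10.1 and a validation marker in section 5.2, and adjudication is blinded to it, so using it in the definition would build in incorporation bias.

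Cost: protocol wording and a second set of class-comparison results. No new data are needed, because the senior-review diagnosis is already collected. The downside is that the senior-review label includes some misdiagnosed patients; the parallel response-confirmed analysis shows how much that matters for the class comparison.

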7.2 Inclusion Criteria

- (i) Able to give informed consent for participation in the study.
- (ii) Male or Female, aged 16 years or above (adult cohort) and 5-15 years for paediatric patients attending the acute care paediatric pathway.
- (iii) Capable (in the opinion of the EMBER clinical research investigator(s) of providing serial breath samples.
- (iv) Diagnosed with acute breathlessness as one of the primary indicator reasons by the clinical acute care team. This is not a requirement for healthy subjects or matched controls.
- (v) One of the indicator provisional diagnoses identified in section 7.1 following senior review by the clinical acute care team. This is not a requirement for healthy subjects or matched controls
- (vi) Able (in the Investigators opinion) and willing to comply with all study requirements.
- (vii) Willing to allow his or her General Practitioner and consultant, if appropriate, to be notified of participation in the study.
- (viii) Ability to understand English.

7.3 Exclusion Criteria

The participant may not enter the study if ANY of the following apply:

Page 20 of 46

- Female participants who are known to be pregnant, lactating or planning pregnancy during the course of the study.
- (ii) Current participation in a clinical trial of an investigative medicinal product or within 3 months or 5.5 half-lives of the IMP whichever is longer.
- (iii) Active or clinically suspected pulmonary tuberculosis
- (iv) In the opinion of the treating physician, breath sampling during the acute admission would be clinically unsafe or inappropriate due to the patient's condition or poor prognosis. Examples include malignancy or autoimmune disease with anticipated survival of under 1 year, and chronic renal replacement therapy.
- (v) Unable or unwilling to give informed consent by visit 1b.
- (vi) Any other significant disease or disorder which, in the opinion of the Investigator, may either put the participants at risk because of participation in the study, or may influence the result of the study, or the participant's ability to participate in the study.

8 STUDY PROCEDURES

A personal legal representative (PeLR) is defined as: A person not connected with the conduct of the trial who is suitable to act as a legal representative by virtue of their relationship with the child and available and willing to do so.

8.3 Informed Consent

Informed consent in acutely unwell patients (both adults and children) poses a number of potential barriers to the conduct of research. However the clinical study team have extensive experience (See Coats TJ *et al* [^{23]}) in consenting both adults and children during acute care settings. During the current study we will recruit participants during the acute phase, with full informed consent from the participant or personal legal representative (PeLR), in the case of paediatrics.

The patient/PeLR must personally sign and date the latest approved version of the informed consent form before any study specific procedures are performed. In the case of paediatric participants they will be asked to complete an assent form, in addition to the PeLR consent form.

Written and verbal versions of the participant information and Informed consent will be presented to the patient/PeLR detailing no less than: the exact nature of the study; the implications and constraints of the protocol; the known side effects and any risks involved in taking part. It will be clearly stated that the patient is free to withdraw from the study at any time for any reason without prejudice to future care, and with no obligation to give the reason for withdrawal. In the event that the participant cannot read the information sheet it will be presented verbally only.

All Informed Consent will be obtained by means of participant dated signature and dated signature of the person who presented and obtained the informed consent. The person who obtains the consent will be suitably qualified and experienced, and have been authorised to do so by the Chief/Principal Investigator as detailed on the Delegation of Authority and Signature log for the study. The original signed form will be retained at the study site within the Trial Master File (TMF) or Investigator Site File (ISF). A copy of the signed Informed Consent will be given to participants/parent/legal guardians and a copy retained in the participant medical notes.

Page 21 of 46

8.2 Screening and Eligibility Assessment

Patients (trial participant groups (i), (ii), (iii), (iv) – see synopsis) will be identified by dedicated member of the research team working across both hospital sites following confirmation of the suspected acute diagnosis once the patient has been clinically reviewed by a senior clinical decision maker.

The research team will be fully ICH-GCP competent and trained in obtaining informed consent and assent according to the hierarchy of consent process outlined in section 8 of this protocol. The research team will use available clinical information systems to confirm the nature of previous admissions and indicator diagnoses such as the UHL-ICE system, iLAB and the radiology systems for pathology and image viewing respectively. Clinical IT systems used to capture clinical meta data are outlined in (Figure 5) below.

Potential participants to the study will be identified shortly after presentation to each of the sites at Glenfield Hospital, Diagnostics Development Unit (DDU)/Children's Assessment Units (CAU) at the Leicester Royal Infirmary, by members of the healthcare team using the inclusi on criteria of the study. Once the decision has been made to admit a patient onto the acute medical unit, potential participants will be approached by a member of the healthcare team and asked if they would like to consider taking part in the study. If the patient is willing to consider participating in the trial, they will be approached by a member of the research team for further information and consent. In many occasions, the healthcare team will also be members of the research team. Due to the nature of acute research the research team will identify themselves with both the clinical nurse responsible for the patient in question on the admissions unit and the clinician(s) responsible so that the consent and screening process can take place in a seamlessness manner and with minimal disruption alongside the patients usual care pathway.

Environment matched adult/spouses/siblings/parents volunteers (trial participants group (v) – see synopsis) will be identified and recruited from a number of sources:

- For acute admission the study team will approach the spouse, parent or sibling of the index case and seek informed consent for study assessments. All healthy subjects will undergo at last two assessments seperated by a duration of up to 6 months to match the acute (visit 1a) and stable state (visit 2) time period elapsed in their index case partner/spouse/sibling/child.
- Additional healthy volunteers will be identified from local recruitment databases and via advertising

Additional patients with chronic asthma, COPD and heart failure (trial participants group (vi) – see synopsis) will be identified via cardiology and respiratory outpatient clinics at Glenfield Hospital, paediatric respiratory outpatient clinics at the Leicester Royal Infirmary, from NIHR Leicester Biomedical Research Centre (BRC) patient research databases and will undergo up to 2 visits over a 6 months period. In all cases permission for recruitment from outpatients will be sought from the responsible consultant for the patient. The rationale for inclusion of this population is to have a stabe state disease control population that have been characterised over the same overall reporting period (stable state for measurements and 2 years for outcome data collection) as the acute population.

Analysis platform

Admissions
coding
(HISS/DW)

Demographics
(PMI)

Pathology
(ILAB/DW)

PFTS
(Expair)

UHL data sources

KEY

UHL data source

EMBER CP component

Figure 5: Clinical informatics organogram

